6.4.2 Secondary Efficacy Endpoints

The secondary efficacy endpoints for this study are as follows:

- Tumor ORR after completion of study treatment, assessed by modified RECIST criteria by breast MRI in *PIK3CA* WT patients.
- Rate of pCR in breast and axilla (total pCR) after completion of study drug in *PIK3CA* WT patients.

These endpoint measures will be summarized by treatment arm and will be analyzed analogue to the primary efficacy endpoint.

The following secondary efficacy endpoints will be performed in all enrolled patients and separated by *PIK3CA* mutation status:

- ORR by clinical breast examination, mammography, and breast ultrasound
- Ki67 values at baseline, Week 3, and surgery (centrally assessed)
- Change in Ki67 from baseline to Week 3; baseline to surgery, and Week 3 to surgery (centrally assessed)
- PEPI score (centrally assessed)
- Change in enhancing tumor volume from baseline to surgery as measured by breast MRI

- Evaluation of different definitions of pCR including the following: a) ypT0, ypN0, and b) ypT0/is, ypNX (breast pCR)

These endpoint measures will be summarized by treatment arm and will be compared between the two treatment arms within each population based on appropriate statistical analyses: ORR will be compared using a Cochrane Mantel-Haenszel test, stratified by tumor size and nodal status; PEPI, Ki67, and tumor volume change will be compared by regression analyses, adjusted for tumor size and nodal status. All secondary endpoints will be tested at a two-sided type I error of 5%.

More details of the analyses will be provided in the Statistical Analysis Plan (SAP).

6.5 SAFETY ANALYSES

Safety analyses will include all patients who received at least one dose of study treatment, with patients allocated to the treatment arm associated with the regimen actually received.

Safety will be assessed through summaries of adverse events, changes in laboratory test results, changes in vital signs, and letrozole and GDC-0032 exposure.

Verbatim descriptions of adverse events will be mapped to thesaurus terms. Adverse event data will be listed by study site, treatment arm, patient number, and study day, severity, relationship to study drug, outcome, and action taken with the study treatments. Events occurring on or after treatment on Day 1 of Week 1 will be summarized by thesaurus term, appropriate thesaurus levels, and NCI CTCAE v4.0 grade. Serious adverse events, including deaths, will be listed separately and will be summarized.

Relevant laboratory and vital sign (heart rate, blood pressure, and temperature) data will be displayed by time, with NCI CTCAE v4.0 Grade 3 and 4 values identified, where appropriate. Additionally, all laboratory data will be summarized in tables by NCI CTCAE v4.0 grade.

6.6 PHARMACODYNAMIC ANALYSES

Ki67 biomarker analyses will include patients with at least one predose and one postdose biomarker assessment, with patients grouped according to the treatment actually received.

6.7 PHARMACOKINETIC ANALYSES

Individual C_{max} and trough plasma concentrations (C_{min}) of GDC-0032 and letrozole from all patients enrolled will be reported. Mean of trough plasma concentrations of GDC-0032 and letrozole will be tabulated. The population pharmacokinetics of letrozole and GDC-0032 in this study will be compared with historical single-agent pharmacokinetics to assess the potential DDI between GDC-0032 and letrozole in this population.

Additional PK analyses on metabolites of GDC-0032, letrozole, and/or other concomitant medications may be conducted as appropriate.

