1.7.1.1 Preliminary Pharmacokinetics

Pharmacokinetic (PK) data are available from 34 patients treated with GDC-0032 at 3, 5, 8, 12, and 16 mg in the ongoing Phase I/II clinical trial (Study PMT4979g). The cohort mean apparent clearance and the terminal half-life ($t_{1/2}$) following a single, oral dose of GDC-0032 had a range of 4.77–9.17 L/hour and 36.7–43.8 hours, respectively. Following daily oral dosing for 8 days, there was a 2- to 4-fold accumulation of GDC-0032. The pharmacokinetics of GDC-0032 appears to be dose linear and time-independent. Preliminary PK data from Cohort E suggest there is no drug-drug interaction (DDI) between letrozole plus GDC-0032. Mean plasma exposure of letrozole when given in combination with GDC-0032 (maximum concentration observed [C_{max}]=0.407 μM and area under the concentration–time curve from 0 to 24 hours [AUC_{0-24}] = 8.01 $\mu\text{M}\cdot\text{hr}$) was comparable with the historical single-agent exposure (C_{max} =0.495 μM and AUC_{0-24} = 10.1 $\mu\text{M}\cdot\text{hr}$) (Awada et al. 2008 [3]). Similarly, plasma concentrations of GDC-0032, when given in combination with letrozole, were within the range predicted by the population PK model. Therefore, letrozole plus GDC-0032 can be co-administered without the risk of a DDI.

GDC-0032 was metabolized primarily by CYP3A4 in human liver microsomes (HLMs) and appeared to be a weak time-dependent inhibitor of CYP3A4. Although in vitro induction studies in human hepatocytes suggested that GDC-0032 has low to moderate potential to induce CYP3A4, preliminary data from the Phase I/II study (PMT4979g) indicate that 9 mg of GDC-0032 daily for 2 weeks in patients had no apparent effect on the pharmacokinetics of midazolam (a sensitive CYP3A4 substrate). Therefore,

[figure not shown]
GDC-0032 may be administered concomitantly with CYP3A4 substrates without the risk of a PK DDI.

For additional details, refer to the GDC-0032 Investigator’s Brochure.

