3. STUDY DESIGN

3.1 DESCRIPTION OF STUDY

This is a two-arm, randomized, double-blind, multicenter, pre-operative study to evaluate the effect of combining letrozole and GDC-0032 versus letrozole and placebo in postmenopausal women with ER+/HER2- untreated, Stage I-III operable breast cancer whose primary tumors are ≥ 2 cm. Patients with cT4 or cN3 tumors are not eligible.

[figure not shown]
Standard of care assessments/procedures (e.g., bilateral mammogram) performed within 28 days of Day 1 dosing do not need to be repeated for screening purposes.

All patients will undergo pretreatment tumor tissue acquisition (snap-frozen [optimal cutting temperature; OCT] and formalin-fixed paraffin-embedded cores [FFPE]). Two pretreatment FFPE core biopsies and one freshly frozen core biopsy must be obtained for all patients prior to beginning study drug treatment. Tumor tissue from prior diagnostic FFPE core biopsies may be used for enrollment eligibility purposes. For the purpose of enrollment, ER, progesterone receptor (PR), and HER2 will be locally determined prior to beginning of study treatment. Remaining tissue will be retained for future translational studies. Pre-surgical sentinel lymph node biopsy (SLNB) is not allowed.

Patients will be randomized into one of the two treatment arms with a 1:1 randomization ratio. Letrozole at 2.5 mg will be dosed once daily plus either GDC-0032 at 6 mg or placebo on a 5–days-on/ 2–days-off schedule for a total of 16 weeks (see [Figure 5](#)). A maximum of 16 weeks of GDC-0032 can be administered. Letrozole can be continued up to surgery per the investigator's discretion.

Figure 5 Study Schema

Letrozole 2.5 mg QD + GDC-0032 6 mg or placebo QD on a 5–days-on/2–days-off schedule

	Pretreatment	Day 15 (Week 3)	Week 9	Week 16	Surgery (Week 17-18)
Tumor tissue	●	●			●
MRI	●		●	●	
Breast U/S	●		●	●	
Mammogram	●			●	

BC = breast cancer; ER+ = estrogen receptor positive; MRI = magnetic resonance imaging; QD = once daily; U/S = ultrasound.

After confirmation of all the eligibility criteria, patients will be randomized to one of the treatment arms. A second biopsy will be performed on Day 15 (Week 3) for biomarker analyses. Biopsies should be performed at least 2 hours after GDC-0032 dose administration.

Randomization will be stratified according to 2 factors:

1. Tumor size (T1-T2 vs. T3)
2. Nodal status (cytologically positive vs. radiologically or cytologically negative)

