3.4.4 Exploratory Outcome Measures

The exploratory outcome measures for this study are as follows:

- ORR, pCR rate, and PEPI scores according to the decrease in Ki67 after 2 weeks of letrozole plus GDC-0032 and letrozole plus placebo.
- Expression of biomarkers before, during, and after therapy. These include, but are not limited to, the following:
 - PI3K pathway aberrations
 - Gene signatures, including intrinsic subtyping and PI3K pathway activity
 - Hormone receptor expression levels
 - Protein and phospho-protein markers and combinations
 - Mutations within cancer-associated genes
 - Copy number alterations in cancer-related genes
 - Plasma-based protein biomarkers
 - ctDNA
- Compare the rates of BCS and conversion to BCS in letrozole plus GDC-0032 versus letrozole plus placebo
- The relationship between GDC-0032 concentration and tumor response and/or drug safety response
- Letrozole concentrations with and without administration of GDC-0032
- The relationship between pharmacogenetic differences in drug metabolizing enzymes and transporters and other patient-specific covariates with PK of GDC-0032 or letrozole and/or drug response
- Changes from baseline to surgery in the apparent diffusion coefficient (ADC), a marker of tumor cellularity derived from diffusion-weighted MRI
- Concordance of the different imaging modalities (MRI [volume, enhancement, diffusion metrics], ultrasound, mammography) in measuring tumor response

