4.2.3 Blinding

Investigators and patients will be blinded to treatment assignment of GDC-0032 or placebo.

If unblinding is necessary for patient management (e.g., in the case of a serious adverse event for which patient management might be affected by knowledge of treatment assignment), the investigator will be able to break the treatment code by contacting the IxRS following approval from the Medical Monitor. Treatment codes should not be broken except in emergency situations where unblinding is needed for treatment decisions. Effort should be made to contact the Medical Monitor before unblinding. Patient treatment assignment may be unblinded at the time the patient discontinues from the blinded treatment phase at the request of the treating physician by contacting the IxRS following approval from the Medical Monitor and stating the reason for unblinding. Unblinding during the study will result in the withdrawal of a patient from the study. For regulatory reporting purposes, and if required by local health authorities, the Sponsor will break the treatment code for all serious, unexpected, suspected adverse reactions that are considered by the investigator or Sponsor to be related to study drug.

While PK samples must be collected from patients assigned to the comparator arm to maintain the blinding of treatment assignment, PK assay results for these patients are generally not needed for the safe conduct or proper interpretation of this trial. The PK assay group will be unblinded to patients' treatment assignments to identify appropriate PK samples to be analyzed and bioanalytical methodology to employ. However, the PK scientist does not have access to the PK assay results and therefore stays blinded until the PK assay results need to be interpreted and reported. Samples from patients assigned to the comparator arm will be analyzed for letrozole. However, GDC-0032 assay will be analyzed by request (i.e., to evaluate a possible error in dosing).

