4.3.2 Dosage, Administration, and Compliance

4.3.2.1 GDC-0032 and Placebo

Patients will receive an oral, daily dose of 6 mg GDC-0032 or placebo on a schedule of 5 days on/2 days off for a maximum of 16 weeks. Patients will take GDC-0032 at the same time of day \pm 2 hours, unless otherwise instructed. Patients will be instructed as to the number of tablets to take. Patients will be asked to record the time and date that they take each dose in a medication diary.

Unless otherwise instructed, GDC-0032 or placebo should be taken on an empty stomach (i.e., approximately 1 hour before or 2 hours after a meal).

If a patient misses a GDC-0032 or placebo dose or vomits up a tablet, she should be instructed to skip that dose and to resume dosing with the next scheduled dose. Missed doses will not be made up. Patients will be instructed to bring their medication diary to

each study visit for assessment of compliance. Patients will also be instructed to bring all unused tablets to each study visit for GDC-0032 or placebo accountability.

Guidelines for dosage modification and treatment interruption or discontinuation are provided in [Section 5.1](#).

Any overdose or incorrect administration of study drug should be noted on the Study Drug Administration eCRF. Adverse events associated with an overdose or incorrect administration of study drug should be recorded on the Adverse Event eCRF.

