Appendix 2 Schedule of Pharmacokinetic Assessments

Visit	Timepoint	PK Assessments
Day 1	3 hours post (± 60 min) letrozole and GDC-0032/placebo administration	Letrozole PK
		GDC-0032 PK
Day 15 (+ 2 days)	0–4 hours prior to letrozole and GDC-0032/placebo administration	Letrozole PK
		GDC-0032 PK
	3 hours (± 60 min) post letrozole and GDC-0032/placebo administration ECG before PK	Letrozole PK
		GDC-0032 PK
Day 57 (+/- 2 days)	3 hours post (± 60 min) letrozole and GDC-0032/placebo administration	Letrozole PK GDC-0032 PK

ECG=electrocardiogram; min=minutes; PK=pharmacokinetics.

Record exact time of dose administration and sample collection.

Appendix 3

Modified Response Evaluation Criteria in Solid Tumors: Assessment of Response of Neoadjuvant Therapy in Early Breast Cancer

Conventional response criteria may not be ideal for the assessment of response in the setting of neoadjuvant therapy in early breast cancer. Therefore, RECIST 1.1 criteria have been modified to specifically address assessment of primary breast lesions along with axillary lymph node disease, using a range of breast imaging modalities. Selected sections from the Response Evaluation Criteria in Solid Tumors (RECIST), Version 1.1¹ are presented below, with modifications and the addition of explanatory text as needed for clarity. For detailed information on the read methodology including how imaging data should be processed prior to reads, please refer to the Study Imaging Charter.

	RECIST v1.1	Modified RECIST Early Breast Cancer Neoadjuvant Therapy
Modalities	CT as primary modality, ultrasound not recommended	No CT; primary assessments by MRI; also assessments by ultrasound, mammography, and clinical exam
Lymph nodes	May be considered target lesions based on size criteria (≥ 15 mm in SAD)	Only axillary lymph nodes assessed; nodes that are considered abnormal on imaging (based on morphological factors including, but not limited to SAD) to be followed as non-target lesions
Possibility of having only non-target disease	Allowed	Not allowed; primary breast lesions must be measurable by MRI and/or ultrasound

CT = computed tomography; MRI = magnetic resonance imaging; SAD = short axis dimension.

BASELINE DOCUMENTATION OF TARGET AND NON-TARGET LESIONS

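### The letrozole interaction analysis in Section 6.7 relies on historical data although a randomised, assayed letrozole-plus-placebo arm is available; GDC-0032 pre-dose summaries and the Day 57 sampling window also need aligning with the 5-on/2-off schedule

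*Protocol*

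**What the plan says.** Section 6.7 (Pharmacokinetic Analyses) reports individual peak and trough concentrations of both drugs and adds: "Mean of trough plasma concentrations of GDC-0032 and letrozole will be tabulated". For the interaction question it names one comparator for both drugs: their population pharmacokinetics "will be compared with historical single-agent pharmacokinetics to assess the potential DDI between GDC-0032 and letrozole in this population".

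Other sections bear on this:

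- Section 3.1: "Patients will be randomized into one of the two treatment arms with a 1:1 randomization ratio". Both arms take letrozole; only one takes GDC-0032.
- Section 4.2.3 (Blinding): "Samples from patients assigned to the comparator arm will be analyzed for letrozole". Placebo-arm samples are assayed for GDC-0032 only on request.
- Section 3.4.4 lists as an exploratory outcome: "Letrozole concentrations with and without administration of GDC-0032".
- Section 4.3.2.1 gives GDC-0032 or placebo as "5 days on/2 days off for a maximum of 16 weeks". Section 4.3.2.2 gives letrozole every day.
- Appendix 2 has four sampling points: 3 hours post-dose on Day 1; "0–4 hours prior to letrozole and GDC-0032/placebo administration" on Day 15 (+2 days); 3 hours post-dose at that same visit; and 3 hours post-dose on Day 57 (±2 days). Exact dose and sample times are recorded.
- Section 1.7.1.1 reports a Phase I comparison of the same kind, in which letrozole exposure with GDC-0032 "was comparable with the historical single-agent exposure".

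**The concern.** The effect of GDC-0032 on letrozole can be estimated here from two concurrently randomised groups with the same visits and sampling times. A comparison with history mixes any interaction with differences in population, assay and study conduct. Section 3.4.4 sets the with-and-without outcome and Section 4.2.3 provides the assays, but Section 6.7 does not carry them into an analysis.

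The question is not empty. Section 4.4.1 says that letrozole is partly metabolised by CYP3A4 and that GDC-0032 may induce that enzyme in vitro, although it had no apparent effect on midazolam in patients. Induction would lower letrozole levels. The Phase I comparison did show lower levels, and a comparison with history cannot say why.

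Separately, the only pre-dose sample and the Day 57 sample appear to have been scheduled without regard to the two off days each week. That affects what a mean GDC-0032 trough describes and whether a post-dose sample can be taken on every permitted day.

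**Working it through.** **Letrozole: the existing historical comparison (Section 1.7.1.1).** Cmax 0.407/0.495 = 0.82; AUC 8.01/10.1 = 0.79. Exposure was 18% and 21% lower than history.

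**Letrozole: precision of the between-arm contrast.** With 330 patients randomised 1:1 (Sections 3.1 and 6.1), n = 165 per arm. The protocol gives no between-patient CV for letrozole, so CV is assumed. On the log scale, SD = √ln(1 + CV²), SE = SD × √(2/n), and the 90% interval is the ratio multiplied or divided by exp(1.645 × SE).

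| Assumed CV | SD (log) | SE, n = 165 | 90% factor |
|---|---|---|---|
| 40% | 0.385 | 0.0424 | 1.07 |
| 60% | 0.555 | 0.0611 | 1.11 |
| 80% | 0.703 | 0.0774 | 1.14 |

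With only 100 evaluable per arm, √(2/100) = 0.141. The factors at CV 40% and 80% become exp(1.645 × 0.385 × 0.141) = 1.09 and exp(1.645 × 0.703 × 0.141) = 1.18. A reduction of the size seen against history (20.7% on AUC) would be detected at two-sided 5% with power of 99%, 92% and 78% at CVs of 50%, 70% and 90% with 165 per arm, or 94%, 74% and 57% with 100 per arm.

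**GDC-0032: check of the model against the protocol's own figure.** Section 1.7.1.1 gives a half-life of 36.7 to 43.8 hours, linear and time-independent kinetics, and 2- to 4-fold accumulation after 8 daily doses. With k = ln 2 / half-life, one-compartment accumulation is (1 − e^(−192k)) / (1 − e^(−24k)) = 2.67, 2.83 and 3.01 at 36.7, 40 and 43.8 hours. All three lie inside the stated range.

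**GDC-0032: the Day 15 visit.** Assume Day 1 opens a 5-day block. This is inferred, and it fits Day 15 having both pre-dose and post-dose samples. Doses then fall on Days 1–5 and 8–12, and Days 13–14 are off. The pre-dose sample on Day 15 is 72 hours after the Day 12 dose. At a 40-hour half-life one day's decay is r = e^(−24k) = 0.660, and in units of one dose:

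- 5-on/2-off, Day 15 pre-dose: (r³ + … + r⁷) + (r¹⁰ + … + r¹⁴) = 0.739 + 0.040 = 0.779.
- Daily dosing, same time: r + … + r¹⁴ = 1.933. Ratio 0.779/1.933 = 0.40 (0.38 to 0.43 over the half-life range).
- Day 16 pre-dose: (0.779 + 1) × 0.660 = 1.174, which is 1.51 times the Day 15 value (1.43 to 1.60).
- Day 17 pre-dose: (1.174 + 1) × 0.660 = 1.434, which is 1.84 times the Day 15 value (1.72 to 1.98).

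The +2-day window therefore lets one mean trough combine samples taken about 72 hours and about 24 hours after a dose. Letrozole is taken daily, so its pre-dose sample is an ordinary 24-hour trough on any of these days.

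**Day 57.** On the same calendar the off days are 6–7, 13–14, and so on to 55–56. The window is Days 55–59, so two of the five permitted days have no GDC-0032 or placebo dose from which to count 3 hours. Appendix 1 gives the Week 9 visit the same ±2 days.

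**The case against.** The strongest reply is that the between-arm contrast is already foreseen. It is a listed outcome, the placebo-arm assays are committed, Section 6.7 covers all enrolled patients and does not call history the only comparison, and Section 6.9 leaves exploratory detail to the SAP. This has some force: the form of the ratio and its interval could properly sit in a SAP. But Section 6.7 does not leave the comparator open. It names one, and for letrozole it is the weaker of the two available.

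A reader might infer more than the protocol supports:

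- That history is the wrong comparator for GDC-0032 too. No arm receives GDC-0032 without letrozole, so there is no concurrent alternative.
- That tabulated GDC-0032 troughs will be set against daily-dosing troughs and produce a false signal. Section 6.7 makes the interaction comparison through population pharmacokinetics, and a model using the recorded times can handle the off days. No direct comparison of tabulated troughs is stated.
- That the Day 15 GDC-0032 sample is not a trough, or should simply be labelled 72 hours post-dose. On the inferred calendar Day 15 is the low point of the week, and a fixed 72-hour label would be wrong for Days 16 and 17 and for patients with dose holds.

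It is also fair that a Day 57 sample without a dose would not meet Appendix 2's own definition, which limits the harm, and that Section 3.3.13 already considers an interaction unlikely.

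**Conclusion.** The point holds for letrozole: Section 6.7 names a non-randomised comparator where a randomised, concurrently assayed one exists and is already a listed outcome. Sections 3.4.4, 4.2.3 and 6.7 need reconciling. The gain is an interaction estimate free of study-to-study differences, with a 90% interval of about ±7% to ±14% if the CV is 40% to 80% and all 165 per arm are evaluable. It would be wider with missing samples, and GDC-0032 holds would dilute the contrast.

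For GDC-0032 the point is narrower. The choice of history stands; only the single mean trough is a poor summary, because the permitted days differ by a modelled factor of up to about 1.8 (assuming Day 1 opens a 5-day block and no doses are held). The Day 57 window conflicts with the dosing calendar on two of five days. All of this concerns an exploratory objective; the co-primary and secondary efficacy conclusions do not depend on it.

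**What to change.** - **Section 6.7, letrozole.** Make the interaction analysis the ratio of geometric mean letrozole concentrations between randomised arms, with a 90% confidence interval, at Day 15 pre-dose, Day 15 3 hours post-dose and Day 57 3 hours post-dose. Keep the historical comparison as context, and cite the Section 3.4.4 outcome so that the sections agree.
- **Section 6.7, GDC-0032.** State that the comparison with history is made through the population model with actual dose and sample times. Summarise pre-dose concentrations by actual time since last dose instead of as one mean trough.
- **Appendices 1 and 2.** Reconcile the ±2-day Day 57 sampling window with the 5-on/2-off schedule in both places. The Week 9 visit in Appendix 1 shares that window with ultrasound, laboratory tests and questionnaires, so changing Appendix 2 alone would leave the two inconsistent.

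The cost is a few sentences in Section 6.7 and one sampling window in two appendices. No new samples or assays are needed.
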